13.2. Statistical and Analytical Plans

A change to the data analysis methods described in the protocol will require a protocol amendment only if it alters a principal feature of the protocol. The SAP will be finalized prior to database lock. Any changes to the methods described in the final SAP will be described and justified in the clinical study report.

13.2.1. General Considerations

All data summaries will be descriptive in nature. Summary statistics for continuous variables will include number of subjects, mean, median, standard deviation, minimum, and maximum. For categorical variables, frequencies and percentages will be provided. When required for the statistical analysis of a particular variable, the baseline value will be the last recorded value prior to the administration of the first dose of study treatment. The exception is the baseline platelet count, which is defined as the average of the two pre-dose values. All confidence intervals will be constructed at the 95% confidence level.

13.2.2. Adjustments for Covariates

It is possible that some potential baseline subject and disease characteristics may impact the interpretation of the efficacy results. Subgroup analyses and regression analyses may be performed to adjust for the potential covariate effects. These analyses will be considered exploratory and, if performed, will be discussed in the clinical study report.

13.2.3. Multicenter Study

This is a multicenter study. Descriptive statistics of the primary efficacy endpoint will be provided for each site to evaluate potential site differences.

CONFIDENTIAL

No use, disclosure or reproduction outside of Omeros without prior written authorization

13.2.4. Multiple Comparisons and Multiplicity

This is a single-arm study with one primary efficacy endpoint. No multiplicity adjustment is necessary.

13.2.4.1. Handling of Missing Data

Unless otherwise specified, statistical analyses will be based on observed data without imputation.

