13.2.4.2. Analysis Populations

The full analysis set (FAS) will include all subjects who receive any amount of study treatment and have at least one post-baseline platelet count. The primary efficacy analyses will be based on the FAS.

The safety analysis set will include all subjects who receive any amount of study treatment. The safety analyses will be based on the safety analysis set.

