13.2.5. Subject Disposition

An accounting of study subjects by disposition will be tabulated. Subjects who discontinued study drug prematurely or withdrew from the study will be summarized and listed, with reason for early termination/withdrawal.

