13.2.8. Primary and Secondary Efficacy Analyses

The plasma therapy-resistant cohort will be the primary subject cohort for the evaluation of efficacy of OMS721. All efficacy analyses will be performed separately for the plasma therapy-resistant cohort and the plasma therapy-responsive cohort. Primary efficacy analyses will be based on the FAS. Supportive efficacy analyses will be based on the safety analysis set.

Definitions of the efficacy endpoints are presented in Section 7.3.

Baseline for platelet count is defined as the average of two tests obtained prior to the first dose of OMS721. If more than two tests are performed, then the two that are most proximate to the first dose of OMS721 should be used. Baseline for other endpoints is defined as the value most proximate to the first dose of OMS721.

CONFIDENTIAL

No use, disclosure or reproduction outside of Omeros without prior written authorization

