13.2.8.1. Analysis of Primary Efficacy Endpoint

The primary efficacy endpoint (platelet count change from baseline) will be summarized descriptively by visit and cohort during the treatment period (induction and maintenance). A repeated measures model with time and baseline platelet count as fixed effects, and subject as random effect will be used to evaluate the primary endpoint by cohort. Time is a categorical variable for the scheduled visit. A generalized estimating equation (GEE) method will be applied to estimate the least-squares mean change from baseline with 95% confidence interval at each scheduled time point.

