- The number and percent of subjects who achieve an increase in eGFR from baseline of $> 15 \text{ ml/min}/1.73 \text{ m}^2$ will be summarized with two-sided exact binomial 95% confidence interval. Subjects whose eGFR cannot be evaluated (e.g., early dropouts or death) will be considered as not achieving the required increase in eGFR.
- The time to increase in eGFR from baseline of $> 15 \text{ ml/min}/1.73 \text{ m}^2$ will be analyzed by the Kaplan-Meier method. Subjects who do not achieve an increase in eGFR from baseline of $> 15 \text{ ml/min}/1.73 \text{ m}^2$ during study will have their event time censored at the last laboratory measurement. Median time to the increase in eGFR from baseline of $> 15 \text{ ml/min}/1.73 \text{ m}^2$ will be estimated with two-sided 95% confidence interval using the complementary log-log transformation [Collett 1994]. The increase in eGFR from baseline of $> 15 \text{ ml/min}/1.73 \text{ m}^2$ rates at 26 weeks, 1 year and 2 years will be estimated with two-sided 95% confidence interval using the Kaplan-Meier method.
- The number and percent of subjects achieving hematological normalization will be summarized with two-sided exact binomial 95% confidence interval. Subjects whose hematological normalization status cannot be evaluated (e.g., early dropouts or death) will be considered as not achieving hematological normalization.
- The time to hematological normalization will be analyzed by the Kaplan-Meier method. Subjects who do not achieve hematological normalization during study will have their event time censored at the last laboratory measurement. Median time to hematological normalization will be estimated with two-sided 95% confidence interval using the complementary log-log transformation [Collett 1994]. The hematological normalization rates at 26 weeks, 1 year and 2 years will be estimated with two-sided 95% confidence interval using the Kaplan-Meier method.
- The number and percent of subjects achieving TMA remission will be summarized with two-sided exact binomial 95% confidence interval. Subjects whose TMA remission status cannot be evaluated (e.g., early dropouts or death) will be considered as not achieving TMA remission.

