13.2.13.9. Rescue Therapy

Subject incidence of use of Rescue Therapy will be summarized by Rescue Therapy type and cohort. Rescue therapies used will be listed by subject.

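### Does the Week-26 platelet mean need a sensitivity analysis for dropout, given that the safety-set repeat cannot supply one?

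*Protocol*

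**What the plan says.** The primary endpoint is platelet change from baseline to Week 26 (Protocol 7.3.1). Section 13.2.4.1 gives the default rule: "statistical analyses will be based on observed data without imputation". Section 13.2.8.1 specifies a repeated measures model with categorical visit and baseline count, in which "subject as random effect will be used to evaluate the primary endpoint by cohort". It then adds: "A generalized estimating equation (GEE) method will be applied to estimate the least-squares mean change from baseline". No working correlation is named.

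Section 13.2.4.2 defines the full analysis set (FAS) as "all subjects who receive any amount of study treatment and have at least one post-baseline platelet count"; the safety set drops the platelet-count condition. Section 13.2.8 adds: "Supportive efficacy analyses will be based on the safety analysis set".

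Several secondary responder endpoints do have a dropout rule. For example: "Subjects whose TMA remission status cannot be evaluated (e.g., early dropouts or death) will be considered as not achieving TMA remission". Section 13.2.8.2 gives the platelet mean no counterpart.

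Section 13.2 leaves a SAP to be finalized before database lock. The SAP that followed is abbreviated because the study was discontinued (SAP 2). It does not analyse the primary objective (SAP 4.1) and performs no efficacy analyses (SAP 9.1).

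**The concern.** A subject who stops study drug keeps only two follow-up visits, 14 and 42 days after the last dose (Protocol 10.1.5), so early stoppers usually have no Week-26 count. If those who leave are doing badly, the mean over those who remain is too favourable, and with no control arm nothing offsets the shift. The only benchmark is the planning null of 45 × 10⁹/L in section 13.1.

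The supportive safety-set analysis looks like a robustness check, but for this endpoint it cannot show anything about dropout. What would be at stake is a platelet response overstated by an unknown amount, with no planned output showing how far the mean moves once leavers are counted.

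**Working it through.** **1. The plan's own figure.** Inputs from Protocol 13.1: true mean 78, null 45, SD 64, two-sided 5% one-sample t-test. The noncentral t gives 96.6% power at n = 56; 90% power needs n = 42 (90.4%). The stated pairing of 56 with 90% is therefore not reproduced, although 56/0.70 = 80 is. That is a separate matter. Its bearing here is that losing 25% of Week-26 values (56 × 0.75 = 42) would still leave 90.4% power, so the question is bias, not power.

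**2. Who lacks a Week-26 value.** Week 26 is Visit 16, Day 183. The last follow-up is 42 days after the last dose, and 183 − 42 = 141. Anyone stopping before Day 141 (about Week 20) has no scheduled visit as late as Day 183. Many later stoppers miss it too: a last dose at Week 22 puts the visits at Weeks 24 and 28.

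**3. Safety set against FAS.** The two sets differ only by treated subjects with no post-baseline platelet count. With no imputation these subjects contribute no change-from-baseline row. Anyone who leaves after one count is in both sets and is handled identically. A check on one simulated data set (56 treated, 4 with no post-baseline count) used the same 52 subjects and 568 rows in both fits:

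| | Safety set | FAS |
|---|---|---|
| Exchangeable GEE, Day 183 | 64.616 | 64.616 |
| Random intercept, Day 183 | 64.613 | 64.613 |
| GEE mean evaluated at the whole set's mean baseline | 64.47 | 64.52 |

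Only the last row differs, by 0.05, and it says nothing about dropout.

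**4. Size of the bias.** n = 56 and SD 64 come from section 13.1; the 12 post-baseline hematology visits from Day 4 to Day 183 come from the schedules in 19.3 and 19.4. Everything else is assumed:
- true mean over all treated 45; failures average 0; three unrelated leavers
- losses spread over Weeks 2–20
- baseline uniform 30–149 × 10⁹/L; slope of change on baseline 0 or −0.5
- within-subject correlation 0.3 or 0.6
- response immediate, or rising linearly to Week 12

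Ranges are over the eight settings, with 1,500 runs each and Monte Carlo error of about 0.2. The middle column is the plain mean of those observed at Week 26, setting aside the unrelated leavers.

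| Scenario | Observed-only mean | Random-intercept fit |
|---|---|---|
| No loss | 45.0 | 44.7–45.3 |
| 11 failures, all leave | 45 × 56/45 = 56.0 | 45.7–53.2 |
| 11 failures, 6 leave | 45 × 56/50 = 50.4 | 45.5–49.0 |
| 6 failures, all leave | 45 × 56/50 = 50.4 | 45.3–49.2 |
| 6 failures, 3 leave | 45 × 56/53 = 47.5 | 45.1–47.0 |

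The repeated-measures fit recovers part of the loss because it uses leavers' earlier counts. With 11 failures averaging −20 and all leaving, it gives up to 54.5, a bias of 54.5 − 45 = 9.5. An independence working correlation, to which a subject random effect does not point, gives 55.6–56.5 with all 11 leaving. The confidence interval half-width is about 16–19 in these settings; the planned value is 2.004 × 64/√56 = 17.1.

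**5. Room before the lower limit reaches 45.** Take the protocol's 78 and SD 64 and set 11 of 56 to a change of 0. The mean is 45 × 78/56 = 62.7. Treating the zeros as data, the combined SD is 65.2 and the limit is 62.7 − 2.004 × 65.2/√56 = 45.2. With the standard error taken from the 45 observed, it is 62.7 − 2.015 × 64/√45 = 43.5.

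| Assigned change | Number set | Mean | Limit, values as data | Limit, SE from observed |
|---|---|---|---|---|
| 0 | 11 | 62.7 | 45.2 | 43.5 |
| −20 | 8 | 64.0 | 45.65 | 45.4 |
| +20 | 16 | 61.4 | 45.35 | 41.0 |

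The largest number tolerated at 0 is 11 under one variance convention and 10 under the other; at +20 it is 16 or 12.

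**The case for a change.** The best case for a change is this. The sponsor evidently thought about dropout, since non-evaluable subjects count as failures for TMA remission and similar endpoints, yet the primary mean was left without protection. Discontinuations are covered ("Subjects who discontinued study drug prematurely or withdrew from the study will be summarized and listed, with reason for early termination/withdrawal") and so is rescue ("Rescue therapies used will be listed by subject"). These show that selective loss happened, not how far it moved the mean. The bias need not be trivial: 9.5 is half of a half-width of 19, and an independence reading of the GEE sentence gives up to 56.5 − 45 = 11.5. One prespecified analysis would need no new patient data.

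All of that stands as description. Four things weigh against acting on it.
- The larger biases need every failing subject to leave. The protocol keeps subjects on rescue in their scheduled visits (7.1), and inclusion criterion 7 limits switching to eculizumab, which would force withdrawal (10.2.2). With about half of the failures leaving, the bias is at most 49.0 − 45 = 4.0.
- The safety-set repeat is labelled supportive for efficacy in general. It is not offered as a test of dropout, and it has a use for responder endpoints, where the denominator can grow.
- Sensitivity analyses are commonly set out in the SAP, which section 13.2 leaves to be finalized before database lock. That stage became an abbreviated SAP because the trial stopped, so silence in the protocol is weak evidence of a planning error.
- Any assigned value (0, −20, +20) is a convention. If failing leavers truly average −20 or +20, assigning 0 gives 48.8–49.0 or 40.8–41.4 against a truth of 45.

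The pairing of a random effect with GEE is a wording question of its own. Reading it as an exchangeable structure is the natural choice, and in the check above the two fits agreed to 0.003 (64.616 against 64.613).

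**Conclusion.** The observations are right and no change follows. The platelet mean has no planned dropout sensitivity analysis, and the safety-set repeat gives essentially the FAS answer for this endpoint. The governing SAP runs neither the primary analysis nor any efficacy analysis, so nothing reported and nothing the trial can conclude depends on the gap. An added sensitivity analysis would leave the primary estimate unchanged.

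The possible bias of a random-intercept fit runs from near 0 to about 8 × 10⁹/L if failing leavers average 0, and to about 9.5 if they average −20, against a half-width of about 16–19. These sizes rest on assumed dropout, leaver means, correlation and baseline spread, none of which the documents give, and the tipping counts depend on the variance convention. If this efficacy plan were reused for another trial, a sensitivity analysis for missing Week-26 counts would be a sensible minor addition in that trial's SAP, with a stated way of counting ineligible subjects and the replacements that section 8.3.2 allows.

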13.2.4.2. Analysis Populations

The full analysis set (FAS) will include all subjects who receive any amount of study treatment and have at least one post-baseline platelet count. The primary efficacy analyses will be based on the FAS.

The safety analysis set will include all subjects who receive any amount of study treatment. The safety analyses will be based on the safety analysis set.

13.2.5. Subject Disposition

An accounting of study subjects by disposition will be tabulated. Subjects who discontinued study drug prematurely or withdrew from the study will be summarized and listed, with reason for early termination/withdrawal.

13.2.6. Subject Characteristics

Demographic, other baseline characteristics, concomitant medications, and aHUS-related therapies (e.g., plasma therapy or renal dialysis) will be listed. Demographics and disease characteristics will be summarized.

13.2.7. Treatment Compliance

Because all IV dosing will be under direct supervision of study personnel, treatment compliance with IV dosing will not be analyzed. Dosing information, including supplemental dosing in conjunction with plasma therapy, will be listed.

Treatment compliance with daily SC dosing will be evaluated using relative dose intensity (Section 13.2.13.1).

13.2.8. Primary and Secondary Efficacy Analyses

The plasma therapy-resistant cohort will be the primary subject cohort for the evaluation of efficacy of OMS721. All efficacy analyses will be performed separately for the plasma therapy-resistant cohort and the plasma therapy-responsive cohort. Primary efficacy analyses will be based on the FAS. Supportive efficacy analyses will be based on the safety analysis set.

Definitions of the efficacy endpoints are presented in Section 7.3.

Baseline for platelet count is defined as the average of two tests obtained prior to the first dose of OMS721. If more than two tests are performed, then the two that are most proximate to the first dose of OMS721 should be used. Baseline for other endpoints is defined as the value most proximate to the first dose of OMS721.

CONFIDENTIAL

No use, disclosure or reproduction outside of Omeros without prior written authorization

13.2.8.1. Analysis of Primary Efficacy Endpoint

The primary efficacy endpoint (platelet count change from baseline) will be summarized descriptively by visit and cohort during the treatment period (induction and maintenance). A repeated measures model with time and baseline platelet count as fixed effects, and subject as random effect will be used to evaluate the primary endpoint by cohort. Time is a categorical variable for the scheduled visit. A generalized estimating equation (GEE) method will be applied to estimate the least-squares mean change from baseline with 95% confidence interval at each scheduled time point.

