7.3. Study Endpoints

7.3.1. Primary Endpoint

- Platelet count change from baseline to week 26

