13. STATISTICS

13.1. Determination of Sample Size

The sample size is based on the plasma therapy-resistant cohort. Assuming that the true mean platelet count change from baseline is $78 \times 10^9 / \text{L}$ with a standard deviation of $64 \times 10^9 / \text{L}$ [Legendre 2013], a sample size of 56 plasma therapy-resistant subjects will provide 90% power to test a null mean platelet count change from baseline of $45 \times 10^9 / \text{L}$ at two-sided significance level of 5% using t-test. It is assumed that 70% of the eligible subjects will be plasma therapy-resistant. Therefore, the total sample size is 80 subjects who meet the full analysis set criteria.

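### Does the primary platelet analysis need rewriting because Protocol Section 13.2.8.1 names neither a working correlation nor the Week 26 test against 45 x10^9/L?

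*Protocol*

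**What the plan says.** - **Endpoint.** Protocol Section 7.3.1: "Platelet count change from baseline to week 26". The schedule places this at Visit 16, Day 183 (26 x 7 + 1). Section 13.2.8 refers to Section 7.3 for the endpoint definitions.
- **Sizing.** Section 13.1 assumes a mean change of 78 and an SD of 64 (x10^9/L), and claims for 56 plasma therapy-resistant subjects "90% power to test a null mean platelet count change from baseline" of 45, "at two-sided significance level of 5% using t-test". It gives no week.
- **Analysis.** Section 13.2.8.1 describes a model with categorical visit and baseline count as fixed effects, "and subject as random effect will be used to evaluate the primary endpoint by cohort". Then: "A generalized estimating equation (GEE) method will be applied to estimate the least-squares mean change from baseline with 95% confidence interval", at each scheduled visit. It states no working correlation, null or success rule.
- **Missing data.** Section 13.2.4.1: "statistical analyses will be based on observed data without imputation", unless otherwise specified. Under Section 13.2.4.2, treated subjects enter the full analysis set (FAS) if they "have at least one post-baseline platelet count"; a Week 26 count is not required.
- **General stance.** Section 13.2.1: "All data summaries will be descriptive in nature".
- **SAP.** Protocol Section 13.2 leaves the SAP to be finalized before database lock. The SAP that exists is abbreviated. Its Sections 4.1 and 9.1 drop the primary analysis and all other efficacy analyses because too few patients were enrolled.

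**The concern.** There is no control arm, so the Week 26 mean change and its lower confidence limit against 45 are the confirmatory result. The section that should define that result does not say which number is compared with 45. Three candidates can be read into the protocol: a t-test on the observed Week 26 counts (from Section 13.1), a GEE interval under some working correlation, or a random-subject model interval.

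These agree when all counts are present and can differ when some are missing. The protocol's own rules allow missing Week 26 counts:

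- After stopping drug, a subject is asked for the two Follow-up visits (Section 8.3.1), the last of them 42 days after the final dose (Section 10.1.5). With the 2-day window, a last dose on Day 136 puts that visit at Day 136 + 42 + 2 = 180 at the latest. The Visit 16 window opens on Day 183 - 2 = 181.
- Several secondary responder endpoints count early dropouts and deaths as failures. The primary endpoint has only the observed-data rule.

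If subjects leave after low counts, an estimator that ignores this would overstate the mean in the drug's favour.

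**Working it through.** **1. The plan's own figure.** Inputs from Section 13.1: difference 78 - 45 = 33, SD 64, n = 56, two-sided 5%. The noncentrality is 33/64 x sqrt(56) = 3.86, and the one-sample t-test has power 96.6%, not 90%. For 90% power, n = 42. The gap is on the safe side. It would fit an unstated 25% loss (42/0.75 = 56), although Section 13.1 counts FAS subjects and gives no loss rate. If only subjects with a Week 26 count are tested, power is 94.7% at n = 50 (10% missing), 90.4% at n = 42 (25%) and 88.1% at n = 39 (30%). The total 56/0.70 = 80 holds. None of these figures depends on the working correlation.

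**2. The comparison can be recovered.** At n = 56 and SD 64 the standard error is 64/sqrt(56) = 8.55. The 95% interval lies above 45 when the observed mean exceeds 45 + 2.004 x 8.55 = 62.1. The Visit 16 interval that Section 13.2.8.1 promises is enough to make this comparison.

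**3. Complete data.** In a simulated trial (n = 56, 12 visits to Day 183), the Week 26 estimate was 93.3 with SE 8.7 under independence, exchangeable and AR(1) working correlations alike.

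**4. Missing data.** The documents give no dropout rate, mechanism or correlation, so all three are assumed here: true Week 26 mean 45, SD 64, dropout depending weakly or strongly on the previous count, three correlation patterns, baseline uncorrelated with change. Bias is in x10^9/L; the last column is the chance that the lower limit exceeds 45 (nominal 2.5%).

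| Estimator | Bias, 10-36% missing | False-positive rate, 10-36% missing |
|---|---|---|
| t-test on observed Week 26 counts | +2.5 to +16.4 | 3.9-35.3% |
| GEE, independence | +2.4 to +17.0 | 4.5-42.5% |
| GEE, exchangeable | -2.9 to +0.5 | 1.0-3.8% |
| Random subject, REML | -3.8 to 0.0 | 0.8-2.0% |
| Unstructured, REML | -0.4 to 0.0 | 1.1-3.1% |

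If dropout is unrelated to counts, every method is within 0.3.

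**5. Which row the text points to.** One random effect per subject with independent residuals gives the same correlation between any two visits, which is the exchangeable structure. With an identity link, the marginal and subject-level means coincide, so GEE and the random-subject model estimate the same quantity. Independence would discard the subject effect that the section names. The t-test appears only under sample size. The relevant rows are therefore the exchangeable GEE and the random-subject fit: within 3.8 of the truth, and mostly low.

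**6. All scheduled visits.** Section 13.2.8.1 covers the whole treatment period. That is 32 post-baseline hematology visits: Day 4 and the 31 maintenance visits. With all 32 visits and about 23-25% missing at Week 26, the exchangeable bias was -0.5 to +0.1, against -1.9 to +0.2 with 12 visits. The lower limit exceeded 45 in 2.5-4.4% of trials.

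**7. The heavier alternative.** Unstructured covariance over 12 visits has 12 x 13/2 = 78 parameters for about 56 subjects. At a true mean of 78 and 25% missing, its power is 91-93%, against 90-97% for exchangeable GEE. If dropout depends on counts never seen (25% missing, strong link), its bias is +3.4 to +3.9, against +0.7 to +3.4. If baseline correlates -0.4 with change, its false-positive rate is 3.6-5.8% at 25% missing.

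**The case for a change.** The strongest case for a change is that a confirmatory rule in a single-arm Phase 3 trial should be written down, and one sentence would do it. The t-test and the exchangeable GEE gave opposite answers against 45 in 7-18% of simulated trials at 25% missing. A different simulation (true mean 78, about 22% missing) averaged 86.3 under independence, 83.1 under AR(1) and 78.5 under exchangeable. A choice left open until the data are in can be made in the drug's favour. Besides early stopping, Section 7.1 lets resistant subjects be dosed before the Shiga toxin, HIV and ADAMTS13 results arrive and then be discontinued; one with a Day 4 count is in the FAS without a Week 26 value.

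What stands: the sentence is absent, and a full SAP should have contained it. What does not stand is the step from there to a changed method:

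- The wide disagreement needs a t-test, independence or AR(1) reading, while the section names a subject effect.
- The primary endpoint does have a missing-data rule, in Section 13.2.4.1.
- Section 13.2.1 speaks of data summaries. Section 13.2.8.1 separates the descriptive summary from the model that evaluates the endpoint.
- Exits are narrower than they look. Relapsing subjects on rescue keep their scheduled visits (Section 7.1), Section 10.1.7 encourages all subjects to complete all evaluations, and inclusion criterion 7 limits the eculizumab route.

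**Conclusion.** No change follows. The working correlation and the explicit Week 26 comparison are details left unsaid, and an analyst can fill them from the protocol: the model's Visit 16 interval in the plasma therapy-resistant FAS, with an exchangeable correlation, set against 45. On that reading the Week 26 bias is about -2.9 to +0.5 x10^9/L with 12 visits and -0.5 to +0.1 with all 32, against a planned margin of 33. The false-positive rate is 1.0-4.4% across these runs, near the nominal 2.5%. These sizes rest on assumed dropout, mechanism and correlation, none of which the documents give. They also assume that dropout depends on counts already seen; if it depends on unseen ones, no option removes the bias.

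Replacing the sponsor's model with an unstructured one is a debatable trade-off: less bias in some scenarios, 78 covariance parameters that may not converge on real data, and no clear power gain. The abbreviated SAP cancels every efficacy analysis, so nothing reported depends on the choice.
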